7.3 Statistical analyses

7.3.1 *Analysis of the primary endpoint*

The primary outcome of this trial will be whether physicians intensified treatment at the visit targeted by the intervention. These data will be collected through EHR data from MGB. We will evaluate the primary outcome using generalized estimating equations (GEE) to adjust for provider-level clustering and multiple patient observations per physician with a logit link function and binary distributed errors; these models will also adjust for the block-randomized design. Because this is a randomized trial, our primary analyses are planned as unadjusted; however, if there are strong predictors of the outcomes not balanced by block randomization, we will adjust for these in the primary analyses. We will conduct analyses using intention-to-treat principles and each intervention arm will be compared to control. Given the nature of the data and how the outcome is being measured, there should not be missing values for our primary outcome.

7.3.2 *Analysis of secondary endpoints*

The secondary outcome of this trial is change in systolic blood pressure control in each arm over 6 months. For this secondary outcome, we will use GEE with an identity link function and normally-distributed errors to account for provider-level clustering, adjusting for the block-randomized design. As in the primary analysis, we will perform analyses unadjusted and adjusted for provider and patient-level covariates to accommodate any imbalance across arms. We will conduct analyses using intention-to-treat principles and each intervention arm will be compared to control. Based on prior studies in a similar local healthcare system, we anticipate approximately 20% missingness rate for the follow-up blood pressure within 6 months, and that this will likely be non-differential between treatment arms.²⁵ Should there be sufficient missing data (e.g., >10%), we will use multiple imputation to handle this. In specific, we will use 20 imputations with Proc MI in SAS to impute any estimated values using fully conditional specification. Analyses will then be conducted on each imputed dataset and combined using Rubin's rules.²⁶ We will perform a complete case analysis as a sensitivity analysis.

7.3.3 *Baseline descriptive analyses*

We will report the means and frequencies of baseline variables for physicians and their eligible patients.

7.3.4 *Subgroup analyses*

In subgroup analyses, we will explore whether there were any modifiers of the effects of the different intervention arms both using standard methods and predictive modeling. For example, we will explore whether providers that score highly on a measure of conscientiousness were more likely to respond to the social norming intervention, or if there were observable differences in patients who were less likely to receive treatment intensification, such as gender or race/ethnicity.

7.3.5 *Exploratory analyses*

Additional exploratory analyses will be performed based on predictive modeling analyses to develop a predictive model for responsiveness to each intervention.

8. Ethical and regulatory requirements

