7.1 Statistical Hypotheses

The null hypothesis is that rates of hypertension treatment intensification will be equal in each of the intervention groups when compared to control.

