7.2 Sample size determination

Because we are selecting specifically for patients with clinical inertia, we expect the control arm rate of medication intensification at the target office visit to be no more than 15%. Assuming an ICC of 0.05, a type I error rate of 5%, and 12 patients per physician over the study period, a sample size of 45 physicians (i.e. 15 per arm) will provide more than 80% power to detect a 15% difference in treatment intensification between each intervention group and control. If the control arm intensification rate is higher than anticipated, we will still be sufficiently powered for reasonable effect sizes (i.e. if the rate of the primary outcome in the control arm was 0.2%, we will be able to detect an effect size of 17%). These data are intended to provide pilot data for larger evaluations, and any positive signal from this pilot trial will help inform next steps. If we have more eligible and

consented physicians than originally anticipated, we will adjust our allocation scheme so that additional physicians are allocated to the control arm to maximize power.

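### With 15 physicians per arm, the GEE analyses name no variance estimator, reference distribution or sidedness; uncorrected sandwich-and-z inference would give about 7% type I error, and corrected two-sided power at the planning inputs is about 71–76%

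*Combined protocol and SAP*

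**What the plan says.** - **Hypothesis (7.1).** The null is that "rates of hypertension treatment intensification will be equal in each of the intervention groups when compared to control". Sidedness is not stated.
- **Sample size (7.2).** The inputs are given as "Assuming an ICC of 0.05, a type I error rate of 5%, and 12 patients per physician over the study period". The claim is that "a sample size of 45 physicians (i.e. 15 per arm) will provide more than 80% power to detect a 15% difference" in intensification between each intervention arm and control. On the control rate: "we expect the control arm rate of medication intensification at the target office visit to be no more than 15" per cent. A second scenario reads: "if the rate of the primary outcome in the control arm was 0.2%, we will be able to detect an effect size of 17" per cent. If more physicians consent than expected, the extra ones go to control.
- **Primary analysis (7.3.1).** "We will evaluate the primary outcome using generalized estimating equations (GEE) to adjust for provider-level clustering and multiple patient observations per physician". The link is logit. On the design, the section adds: "these models will also adjust for the block-randomized design". Each intervention arm is compared with control, and strong unbalanced predictors may be added to the model.
- **Secondary analysis (7.3.2).** Systolic blood pressure is analysed by identity-link GEE with the same clustering. About 20% missing values are expected, handled by 20 imputations and Rubin's rules, with complete cases as a sensitivity analysis.
- **Recruitment (4.3 and 4.3.2).** At least 100 physicians are expected to be eligible and about half, or at least half, to agree. The target is 45.

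Neither 7.3.1 nor 7.3.2 names a working correlation, a variance estimator, a small-sample correction or a reference distribution. They also do not say whether the design adjustment means the three session strata or the individual blocks of three.

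**The concern.** The physician is the unit of randomization, so each contrast rests on 30 independent units however many patients they see. The usual GEE sandwich variance is biased downward with so few clusters, and a normal reference ignores the uncertainty in that variance. Both push the false-positive rate above the nominal level.

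The unstated option can decide a result. In simulation at the planning inputs, 3.7–5.0% of comparisons at 15% versus 30%, and 1.6–2.2% under the null, are significant with the uncorrected sandwich and z but not with KC and t. Section 7.2 says that "any positive signal from this pilot trial will help inform next steps", so a false signal would have a use even in a pilot. The correction also costs power, and the stated 80% is borderline at its own inputs before any correction.

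**Working it through.** **Inputs from 7.2:** 15 physicians per arm, 12 patients each, ICC 0.05, 5% type I error, 15% versus 30%. **Assumption:** two-sided tests, because the null is equality.

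**1. The plan's own power figure.**
- Design effect: 1 + (12 − 1) × 0.05 = 1.55. Effective patients per arm: 15 × 12 / 1.55 = 180 / 1.55 = 116.1.
- Unpooled SE: √[(0.15 × 0.85 + 0.30 × 0.70) / 116.1] = √(0.3375 / 116.1) = 0.0539.
- Pooled SE: √(2 × 0.225 × 0.775 / 116.1) = 0.0548.
- Unpooled power: Φ(0.15 / 0.0539 − 1.96) = Φ(0.82) = 79.5%.
- Pooled power: Φ[(0.15 − 1.96 × 0.0548) / 0.0539] = Φ(0.79) = 78.5%.
- One-sided 5%, pooled: 86.7%.

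The stated figure is reproduced to within 2 points, but neither two-sided formula exceeds 80%. The closed-form requirement is 121 × 1.55 / 12 = 15.6 physicians per arm.

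**2. Type I error, analytic.** With 15 equal clusters per arm, the uncorrected sandwich variance is too small by a factor of 14/15. Its size with z is P(|t₂₈| > 1.96 × √(14/15)) = P(|t₂₈| > 1.894) = 6.9%.

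**3. Simulation.** Beta-binomial data, logit GEE, 12 patients per physician, ICC 0.05; 20,000 null runs (15% in every arm) and 10,000 runs at 15% versus 30%. Degrees of freedom (df) for t are physicians minus model parameters. Monte Carlo SE is at most about √(0.07 × 0.93 / 20,000) = 0.2 points for size and √(0.76 × 0.24 / 10,000) = 0.4 points for power.

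| Model | df | Size: uncorrected z | Size: uncorrected t | Size: KC, t | Size: MD, t | Power: uncorrected z | Power: KC, t | Power: MD, t |
|---|---|---|---|---|---|---|---|---|
| Two-arm, arm only | 28 | 6.7% | 5.6% | 4.8% | 4.1% | 79.7% | 75.2% | 72.7% |
| Two-arm, strata | 26 | 7.8% | 6.5% | 4.9% | 3.5% | 82.0% | 75.2% | 70.6% |
| Three-arm, arm only | 42 | 6.7% | 5.9% | 5.1% | 4.3% | 80.1% | 76.3% | 73.8% |
| Three-arm, strata | 40 | 7.3% | 6.4% | 5.0% | 3.8% | 81.3% | 76.2% | 72.4% |

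A t reference without a variance correction is not enough. The result is not sensitive to the ICC: uncorrected z gives 6.7–7.4% at ICC 0.02 and 7.1–7.7% at ICC 0.10.

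**4. Uneven physician volumes (assumption; eligibility needs only 2 qualifying patients).** At a coefficient of variation (CV) of 0.7, size is 7.9–9.0% for uncorrected z, 5.9–6.0% for KC with t and 4.2–4.8% for MD with t. Power is about 71–72% with KC and 66–69% with MD.

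**5. Conditions under which corrected power reaches 80%.**
- *Lower control rate.* At 12% versus 27%, KC gives 80.0–80.4%. At 10% versus 25%, KC gives 83.6–83.7% and MD 80.6–81.8%.
- *Extra control physicians.* 100 eligible × 50% = 50 physicians, so 20 control and 15 per intervention arm. At 15% versus 30% in an arm-only model, uncorrected gives 85.2%, KC 81.9–82.6% and MD 80.3–80.9%.
- *One-sided 5%.* KC power is 85.6% at 15% versus 30%. Size is then 6.2–6.7% uncorrected and 5.1% with KC.

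**6. Second scenario,** reading 0.2% as 20% (assumption), so 20% versus 37%: formula 82.3–83.2%, KC about 79–80%, MD 75.7–77.3%.

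**7. Systolic pressure,** complete cases, 20% missing at random, ICC 0.02–0.10 (assumed): uncorrected z 6.8–7.7%, KC with t 5.3–5.4%. This matches the planned sensitivity analysis; the multiply imputed analysis was not simulated.

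**The case against.** A reader might infer that the trial will run at 7% type I error. The documents do not support that. They never say that an uncorrected sandwich with z will be used, and they do not exclude model-based standard errors, for which a run with t on 28 df gave about 5.5%. The size figure is conditional on ordinary GEE inference.

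A reader might also infer that the trial is underpowered, or that its power claim has no room for a correction. That goes too far. Section 7.2 treats 15% as an upper bound on the control rate, and KC reaches 80% at about 12%. Sections 4.3 and 4.3.2 imply at least 50 consenting physicians, and 7.2 sends extras to control; that restores 80% under either correction in an arm-only model, although stratum terms would lower MD somewhat. This is a contingency, since 45 remains the target. A one-sided test would also have room, but nothing in the plan says one-sided.

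The excess is about 2 points per comparison, in a self-described pilot, and KC is itself near 6% when volumes are very uneven. All of this limits the consequence. It does not supply the missing specification, and it leaves the power figure at 45 physicians and 15% versus 30% unmet for a two-sided test.

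**Conclusion.** The point holds in conditional form and should be fixed. The omission is certain. If ordinary sandwich-and-z inference fills it, two-sided type I error is about 7% per comparison (6.7–7.8%) against the stated 5%, and higher with uneven volumes. At exactly 45 physicians and a 15% control rate, two-sided power for a 15-point difference is 78.5–79.5% by formula, about 75–76% with KC and t, and about 71–74% with MD and t. These figures rest on two-sided tests, 12 patients for every physician and ICC 0.05. Power of 80% is within reach under the conditions in step 5, so the finding is that the claim needs its conditions stated, not that the design fails.

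**What to change.** **7.3.1.** Prespecify, before outcome data are examined:
- an exchangeable working correlation and two-sided 5% tests;
- one named small-sample-corrected sandwich. KC keeps more power and holds about 5% when volumes are similar; MD is the safer choice if volumes are expected to be very uneven;
- a t reference on physicians minus parameters for the model actually fitted: 42 or 40 df for one pooled three-arm model (without or with stratum terms), 28 or 26 for separate two-arm models, fewer if covariates are added;
- design adjustment for the three session strata. Adjustment for individual blocks was not simulated, but 45 / 3 = 15 blocks would use many more parameters.

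**7.3.2.** Use the same corrected variance within each imputed dataset. Combine by Rubin's rules with small-sample degrees of freedom based on the physician-level complete-data df, rather than a fixed 42 or 40.

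**7.2.** State sidedness. Restate power at 45 physicians and 15% versus 30% as about 75–76% (KC) or 71–74% (MD), and give the conditions under which 80% is reached.

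**Cost.** Wording and one variance option; no new data and no change to enrolment. Confidence intervals widen by about 7–9% (KC) or 10–16% (MD), and nominal power at 15% versus 30% falls by about 4–9 points, so more true signals would be missed.

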5.3 Measures to minimize bias: randomization and blinding

Physicians will be informed about the study and agree to participate using an online consent process through RedCap, and then will be asked to complete a set of behavioral surveys also administered through RedCap. PCPs will then be randomized to one of the two intervention arms

or the control arm. To minimize imbalance between treatment groups, we will use block stratified randomization. Based on the number of sessions per week, providers will be determined to have a small (1-2 sessions), medium (3-4 sessions), or large (5 or more sessions) panel. Within each stratum, we will array physicians into blocks of 3 (note: could also be multiples of 3). All possible balanced combinations of assignment within the block will be allowed in each stratum. Ultimately, within each block and each stratum, physicians will have an equal probability of being assigned to one of the 3 arms.

It will not be possible to blind physicians to the interventions, as they will directly receive either e-consults, dashboards, or no intervention. Because physicians have individual panels, hypertension is typically treated via routine follow-up visits with the PCP, and the interventions are specific to each physician, risk of practice-level contamination is low.

6. Study Assessments and Procedures

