6.1 Baseline data

We will collect baseline data using a combination of provider surveys and the EHR. From the provider surveys, we will collect physician age, gender, race/ethnicity, years in practice, practice location, and the behavioral scales detailed below. We will also collect data on providers from the EHR, including, but not limited to: hypertension prescribing trends (frequencies of medications utilized, BP control rates, time to treatment intensification) and information about the PCP's panel such as panel size, demographic characteristics (e.g. age, gender, race/ethnicity), and clinical characteristics (e.g. comorbidities). We will also collect data specific to the patients who meet the definition for clinical inertia and whose visits are targeted by the interventions. This will include sociodemographic data, medical history and comorbidities, baseline resource utilization in prior 12 months (i.e., number of visits), and biometric values (e.g., serum creatinine, systolic/diastolic blood pressures).

The surveys that physicians will complete were selected to capture personality traits and behavioral tendencies that might contribute to clinical inertia or intervention responsiveness.

These surveys will include measures of:

- risk aversion (Physicians' Reactions to Uncertainty Scale)¹⁷
- long and short term orientation (Individual Cultural Values Scale)¹⁸
- conscientiousness (Ten-Item Personality Inventory)¹⁹

- need for cognition (Need for Cognition Scale)²⁰
- resistance to change (Resistance to Change Scale)²¹
- susceptibility to social norms (Social-Norm Espousal Scale)²²
- burnout (Professional Fulfilment Index)²³
- automaticity (Self-Report Behavioural Automaticity Index).²⁴

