6.2 Outcomes

The *primary outcome* will be whether physicians intensified treatment at the visit targeted by the intervention. Intensification of treatment will include an increase in dose of an existing antihypertensive medication, adding an additional medication, or rotation of one medication to another that is stronger or more appropriate for the patient (e.g. changing hydrochlorothiazide to furosemide for a patient with chronic kidney disease). These will be measured using prescribing information from the EHR on the day of the patient's visit.

The *secondary outcome* will be the change in systolic blood pressure over 6-months of follow-up in each intervention arm compared to control. The initial value will be the systolic blood pressure at the time of enrollment that determined the patient's eligibility for participation. The follow-up blood pressure will be the last blood pressure available in the EHR within 6 months after the visit targeted by the intervention. Based on prior studies in a similar local healthcare system, we anticipate approximately 20% missingness rate for the follow-up blood pressure within 6 months, and that this will likely be non-differential between treatment arms.²⁵ Should there be sufficient missing data (e.g., >10%), we will use multiple imputation to handle this. In specific, we will use 20 imputations with Proc MI in SAS to impute any estimated values using fully conditional specification. Analyses will then be conducted on each imputed dataset and combined using Rubin's rules.²⁶ We will perform a complete case analysis as a sensitivity analysis.

Each post-intervention interview will be moderated by trained study staff using a semi-structured interview guide that asks physicians about barriers to hypertension treatment intensification, perspectives on different intervention arms, and suggestions for improvement.

We will use results from the physician interviews and study staff expertise to select variables for inclusion in the predictive modeling analysis. These variables will all be available in either the EHR or baseline physician surveys and will include, but are not limited to: physician age, gender,

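### Section 7.3.1 lets unnamed, imbalanced 'strong predictors' enter the primary model with no list, threshold or lock point, and 7.3.2 does not rank its two SBP analyses or plan baseline SBP as a covariate (minor)

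*Combined protocol and SAP*

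**What the plan says.** Section 7.3.1 fixes most of the primary model: a GEE with logit link, provider-level clustering, adjustment for the randomisation design, intention to treat, and each intervention arm compared with control. It gives a default, "Because this is a randomized trial, our primary analyses are planned as unadjusted", and one exception: "if there are strong predictors of the outcomes not balanced by block randomization, we will adjust for these in the primary analyses". The exception changes the primary analysis itself; it does not add a sensitivity analysis.

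No other section narrows the exception.
- Section 7.3.3 says only "We will report the means and frequencies of baseline variables for physicians and their eligible patients".
- Section 6.1 names about 21 physician-level items (5 survey characteristics, 8 behavioural scales, 3 prescribing measures, panel size, 3 panel demographics, and comorbidities), and the list is open: "We will also collect data on providers from the EHR, including, but not limited to: hypertension prescribing trends". Patient-level data come on top.
- The one rule for choosing variables, in section 6.2, serves another purpose: "to select variables for inclusion in the predictive modeling analysis".

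For SBP, section 7.3.2 says "we will perform analyses unadjusted and adjusted for provider and patient-level covariates to accommodate any imbalance across arms". Section 6.2 defines the baseline for the change score: "The initial value will be the systolic blood pressure at the time of enrollment". Section 6.1 lists blood pressure among the patient values collected. No section names baseline SBP as a model covariate.

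**The concern.** Two analysts who both follow 7.3.1 can put different covariates in the primary model, because neither 'strong' nor 'not balanced' is defined. That remains true if both choose from the baseline table alone and never look at outcomes. The plan also sets no point before outcome review at which the choice is closed. At stake is which odds ratio and p-value count as the primary result.

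For SBP the plan produces two results without saying explicitly which is the main one. It also does not commit to the one patient covariate most likely to sharpen the estimate.

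**Working it through.** **Inputs from section 7.2:** 15 physicians per arm, 12 patients each, ICC 0.05, control rate 15%, difference 15 points, alpha 5% (two-sided assumed).

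**Assumed, because the plan gives no figures:** 2 or 4 candidate physician-level covariates; R2 0.05 each; lenient and strict imbalance cut-offs of 0.25 and 0.50 standardised difference; where strength is judged on trial data, correlation cut-offs of 0.20 and 0.36. Total R2 of 0.10-0.20 lies inside the share of physician-mean variance that is truly between physicians, 12 x 0.05 / 1.55 = 0.387.

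**1. The plan's power.** Design effect 1 + 11 x 0.05 = 1.55, so effective n per arm is 180/1.55 = 116.1. SE = sqrt((0.15 x 0.85 + 0.30 x 0.70) x 1.55/180) = 0.0539 and z = 0.15/0.0539 = 2.78. Power is 78.5% (pooled variance), 79.5% (unpooled) or 76.6% (t, 28 df), close to the stated figure of more than 80%. This only sets the effect size for the simulations.

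**2. Chance imbalance alone.** The standardised difference divided by sqrt(2/15) is referred to t with 28 df.
- Above 0.25: 0.499 per covariate; at least one of 2 or 4: 1 - 0.501^2 = 0.75 and 1 - 0.501^4 = 0.94.
- Above 0.50: 0.182 per covariate; at least one of 2 or 4: 0.33 and 0.55.

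**3. Imbalance and strength together,** as the clause requires (10,000 runs, correlation taken within arms). The lenient pair (0.25 and 0.20) fires in 49% of trials with 2 candidates and 73-74% with 4. The strict pair (0.50 and 0.36) fires in 8% and 15%.

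**4. Do the two readings reach different verdicts?** Entries are for 2 / 4 candidates. The linear model uses physician means (10,000 runs). The GEE check uses the logit link, the Mancl-DeRouen variance and a t reference (5,000 runs, strata omitted).

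| How covariates are chosen | Model | Planned effect | Null |
|---|---|---|---|
| Predictors named from prior knowledge, balance only | linear | 4.1 / 7.9% | 1.5 / 2.4% |
| Same | GEE | 5.2 / 9.4% | 1.0 / 2.1% |
| Strength judged on trial outcomes | linear | 4.8 / 8.5% | 1.8 / 3.4% |
| Same | GEE | 6.1 / 9.9% | 1.4 / 2.5% |

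Type I error under any single reading is 3.1-5.6%. Power is 73-77% unadjusted and 68-78% with triggered adjustment, so dropping the trigger costs no clear power. In the GEE check, when the selections differ, the median change in the odds ratio is 7-14%. The SE of the log odds ratio is sqrt(1.55 x (1/(180 x 0.15 x 0.85) + 1/(180 x 0.30 x 0.70))) = 0.33, so this shift, ln 1.07 = 0.07 to ln 1.14 = 0.13, is 0.2-0.4 SE.

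**5. Baseline SBP.** Assume baseline and follow-up SBP have SD 15 and correlation rho before selection, the baseline mean is 140, and patients enter with SBP of at least 140. Selection cuts baseline variance to v = 1 - 2/pi = 0.363 of its full value. Ignoring clustering, the variance with baseline as covariate relative to the plain change score is (1 + rho) / ((1 + rho) + (1 - rho)v):
- rho 0.3: 0.836, SE 8.5% smaller
- rho 0.5: 0.892, SE about 5.5% smaller
- rho 0.7: 0.940, SE 3.1% smaller

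The goal is below 140/90, so diastolic pressure alone may qualify a patient. With a diastolic mean of 78-86, SD 10 and correlation 0.6 with SBP (all assumed), the gain becomes about 3-12%.

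**The case against.** The strongest case against is that this is a wording point in a pilot. Adjusting for a strong imbalanced predictor is sensible practice, the default is stated, and section 7.2 says the data are meant to inform larger evaluations. The shift of 0.2-0.4 SE is small against sampling error. The cut-offs, R2 and number of candidates are not in the plan, and the disagreement rates depend on how far apart the two readings are set. The simulations use two arms and physician-level covariates only. All of this stands, and it limits the severity.

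Four stronger readings are tempting, and the documents support none of them.
- *The clause inflates type I error.* Error rates of 7.4% (3 candidates) and 9.7% (8 candidates) do appear in simulation, but only when the analyst may take the smallest p-value among several models. Section 7.3.1 does not license that, and nothing shows that outcomes will guide the choice.
- *The clause will usually apply.* The 75-94% in step 2 counts imbalance above 0.25 alone. The clause also requires strength, and on a strict reading the two coincide in only 8-15% of trials.
- *Baseline SBP is excluded.* Section 7.3.2 allows patient-level covariates and SBP is collected, so it could enter the adjusted analysis. It is simply not planned.
- *Omitting baseline SBP biases the SBP comparison.* Randomisation protects the contrast either way.

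It is also fair to read the opening words of the sentence on adjustment in 7.3.2 as carrying over the unadjusted default. That is an inference, however, and the default it would carry over itself gives way when imbalance is found.

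**Conclusion.** The point holds as a minor one. The primary model is not fully determined before outcomes can be seen, since neither term in the exception is defined and no lock point is set. Under the assumed inputs, verdicts diverge in about 4-10% of trials at the planned effect and 1-3% under the null, per comparison with control, without material type I inflation. How often the trigger fires, 8-15% or 49-74%, depends mainly on how strictly the clause is read, which is itself the ambiguity.

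For SBP, the two analyses are not explicitly ranked and an available precision gain of about 3-9% in the standard error is not secured. That range rests on the assumed rho of 0.7 to 0.3, SD 15, mean 140 and entry at 140 or above.

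**What to change.** **Section 7.3.1.** Make one model primary whatever the observed balance: the logit GEE with arm and the design adjustment already planned. State that adjustment as the session stratum, which section 5.3 defines as "small (1-2 sessions), medium (3-4 sessions), or large (5 or more sessions) panel". This is one reading of adjusting for the block-randomised design, and the plan should say that it is the one meant. Allow further covariates only if they are named before outcome data are reviewed; a sponsor who wants protection against chance imbalance can name them then. Report adjustment for observed imbalance as a labelled sensitivity analysis.

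**Section 7.3.2.** Make the main analysis the identity-link GEE with arm, session stratum and baseline SBP as a covariate. Keep the version without baseline SBP, and any imbalance-driven adjustment, as labelled sensitivity analyses.

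**Cost.** Wording only. Session counts and baseline SBP are already collected, and sample size and procedures do not change. With baseline SBP in the linear model, the arm estimate is the same whether follow-up SBP or change is the response, so the secondary endpoint stays as defined.

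### The SBP analysis accounts for physician clustering, but nothing in the plan carries that clustering into the imputation that will feed it

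*Combined protocol and SAP*

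**What the plan says.** Section 7.3.2 analyses change in SBP over 6 months with "GEE with an identity link function and normally-distributed errors to account for provider-level clustering", comparing each intervention arm with control.

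On missing data, section 6.2 states that "we anticipate approximately 20% missingness rate for the follow-up blood pressure within 6 months", and 7.3.2 repeats this. The rule is: "Should there be sufficient missing data (e.g., >10%), we will use multiple imputation to handle this". The method is: "we will use 20 imputations with Proc MI in SAS to impute any estimated values using fully conditional specification". Then: "Analyses will then be conducted on each imputed dataset and combined using" Rubin's rules. Finally: "We will perform a complete case analysis as a sensitivity analysis".

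Neither section lists the variables in the imputation model. Neither says whether physician, arm or session stratum is among them, or at what level the imputation is done.

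**The concern.** Patients of one physician share a physician effect, and the GEE widens the standard error to allow for it. If the imputation model does not know the physician, an imputed patient is drawn around the arm mean given the covariates and carries no physician effect. The completed data then show less within-physician correlation than the real data, and the cluster-robust variance computed from them is too small. Rubin's between-imputation term does not make up the difference.

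The other ordinary choice, physician as a class variable, errs in the opposite direction. Each physician's mean is estimated with no pooling, and the noise in those means adds to the apparent between-physician variance.

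This is the expected path, because the 20% forecast is twice the 10% trigger. SBP change is the only secondary outcome, and section 7.2 presents the trial as a source of pilot data for larger evaluations. Its interval, and any SBP ICC taken from the completed data, may therefore be carried forward. Leaving the imputation model open also leaves a choice, possibly made after the data are seen, that moves the standard error in either direction.

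**Working it through.** **Inputs from the plan.** 15 physicians per arm; "Assuming an ICC of 0.05, a type I error rate of 5%, and 12 patients per physician over the study period" (section 7.2); 20% missing and 20 imputations (sections 6.2 and 7.3.2).

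**Assumptions.** The plan gives no ICC for SBP. The 0.05 belongs to the binary primary outcome, so other values are shown. Clusters are equal, and data are missing completely at random in the closed form and in simulation A. Total variance is set to 1, since the ratios do not depend on it.

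**The plan's own figure.** No standard error or power is stated for SBP. The only clustered figure is the primary power of more than 80%. The design effect is 1 + 11 × 0.05 = 1.55, and the effective n per arm is 180/1.55 = 116.1. For 15% against 30% this gives power of 78.5% (pooled variance) or 79.5% (unpooled). That is within two points of the stated figure, so the inputs are being read as the plan intends.

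**Closed form, physician omitted** (arm in the model, no other covariate, variance of one arm mean, ICC 0.05):
- Both members of a within-physician pair are observed with probability 0.8 × 0.8 = 0.64. The ICC in the completed data is about 0.05 × 0.64 = 0.032.
- Within-imputation variance: (1 + 11 × 0.032)/180 = 0.00751.
- Between-imputation variance: 0.2² × (1/36 + 1/144) = 0.00139. Times 1 + 1/20, this is 0.00146.
- Rubin total: 0.00897.
- True variance: 144 observed patients with design effect 1 + 8.8 × 0.05 = 1.44, where 8.8 is the mean number of other observed patients with the same physician (11 × 0.8). This gives 1.44/144 = 0.0100.
- SE ratio: √(0.00897/0.0100) = 0.947.

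The same steps give 0.977 at ICC 0.02 and 0.915 at ICC 0.10.

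**Closed form, physician as fixed effects** (ICC 0.05; on average 9.6 observed and 2.4 missing per physician):
- Variance of an observed physician mean: 0.05 + 0.95/9.6 = 0.1490.
- Extra variance from imputing: 0.2² × 0.95 × (1/9.6 + 1/2.4) = 0.0198.
- Within-imputation variance: (0.1490 + 0.0198)/15 = 0.01125. Between-imputation: 1.05 × 0.0198/15 = 0.00139. Total: 0.01264.
- True variance: 0.1490/15 = 0.00993. SE ratio: √(0.01264/0.00993) = 1.128.

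**Simulation A** (null, three arms, 20 imputations, one patient covariate explaining 25% of within-physician variance, cluster-robust linear model, 20,000 runs per row). Cells show the ratio of mean combined SE to true SD, then type I error using t(42):

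| ICC, missing | Physician omitted | Fixed effects | Random intercept | Complete case |
|---|---|---|---|---|
| 0.01, 20% | 0.983, 5.4% | 1.146, 2.6% | 0.999, 5.1% | 1.001, 5.5% |
| 0.05, 10% | 0.966, 5.9% | 1.051, 4.1% | 0.998, 5.1% | 0.998, 5.2% |
| 0.05, 20% | 0.942, 6.1% | 1.108, 3.0% | 1.000, 4.8% | 1.000, 5.2% |
| 0.10, 20% | 0.919, 7.2% | 1.092, 3.4% | 1.011, 4.9% | 1.009, 5.0% |

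With a normal reference in place of t(42), type I error with physician omitted at ICC 0.05 and 20% missing is 7.0%. In this simulation the random-intercept imputation took the variance components as known.

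**Simulation B** (missing at random, baseline correlation 0.4, bias-corrected cluster variance, t(28), variance components estimated for the random intercept):
- Physician omitted: SE 6% too small and type I error 6.1% at ICC 0.05; 8% too small and 6.8% at ICC 0.10; negligible at ICC 0.02.
- Fixed effects: SE 10-13% too large, type I error 2.4-2.7%.
- Random intercept: SE ratio 1.00.
- Complete case: SE ratio 0.99-1.00, type I error 5.2-5.3%.

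A further simulation at ICC 0.05 put the shortfall with physician omitted at about 6-8% and the excess with fixed effects at about 13%.

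**The case against.** The strongest reply is that the plan leaves the imputation model open and does not commit to a wrong one. A reader might infer that the plan prescribes single-level imputation and that its standard errors are therefore wrong. The documents do not support that. They name a procedure, a specification and a number of imputations, and are silent on the variables. Any error depends on how the gap is filled.

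A reader might also infer that the named procedure must give wrong standard errors however it is used. That does not stand either. A simulation of ordinary imputation with one added covariate, the mean follow-up SBP of the physician's other observed patients, gave an SE ratio of 0.99 and type I error of 5.0% at ICC 0.05, and 0.98 and 5.3% at ICC 0.10. Section 6.1 plans to collect physician-level data, such as BP control rates, that could partly serve this purpose. But nothing in the plan commits to such a covariate, and the two routine choices both miss.

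Three further points limit the concern:
- The size is modest. At ICC 0.05, type I error rises by about one to two percentage points, and fixed effects err on the conservative side.
- A complete-case analysis is already planned and had correct standard errors in these simulations. It does not follow that it should lead. If missingness depends on patient factors, an unadjusted complete-case estimate can be biased, which is the usual reason for imputing.
- The documents state no degrees of freedom for the combined test, so they give no basis for a separate criticism on that score.

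**Conclusion.** The concern holds as a gap with a modest, calculable consequence. The plan clusters the SBP analysis by physician but has nothing that carries clustering into the imputation, and by its own forecast the imputed analysis will be the main one.

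At 15 physicians per arm, 12 patients each, 20% missing and an SBP ICC of 0.05, omitting physician makes the combined standard error about 6-8% too small, with type I error of about 6-7%. Physician fixed effects make it about 10-13% too large. The shortfall is about 2% at ICC 0.02 in the closed form and about 8% at ICC 0.10 in both simulations. These figures rest on an SBP ICC that the plan does not give and on equal clusters. Because physicians qualify with as few as 2 eligible patients, fixed-effects imputation could also be unstable for the smallest panels.

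A reader might extend this to the primary outcome. The documents do not support that, since section 7.3.1 expects no missing values there.

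**What to change.** In 7.3.2, and in the matching text of 6.2, state that missing follow-up SBP is imputed from a model with a random physician intercept that includes arm, session stratum, baseline SBP and intensification at the targeted visit. Keep the physician-clustered complete-case analysis as the sensitivity analysis. Settle this wording before outcome data are seen.

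The cost is revised SAP text and a different imputation routine; no new data are needed. The interval will be slightly wider than one from imputation that ignores physician. In simulation A at ICC 0.05 and 20% missing, the mean SE was 2.091 against 1.971 (on an assumed SD of 15 mmHg for SBP change), a ratio of 2.091/1.971 = 1.06.
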